### **4.3. Randomization Criteria**

The following criteria must be met to be eligible for randomization:

1. There have been  $\leq 3$  IR rescue episodes per day for breakthrough pain from Day -3 to Day -1 during the Baseline Assessment Period.
2. The mean value of the average daily pain scores for the index bone metastasis cancer pain site from Day -5 to Day -1 during the Baseline Assessment Period must be  $\geq 5$ ; Subjects must complete interactive response technology (IRT) pain assessments on at least 3 of the 5 days during the Baseline Assessment Period.
3. There are no intolerable opioid side effects in the judgment of the subject from Day -3 to Day -1 during the Baseline Assessment Period.
4. The Patient's Global Assessment of Cancer Pain must be "fair", "poor" or "very poor" at the Baseline Visit.
5. Radiologic eligibility must have been confirmed by the Central Reader during the Screening Period, Baseline Assessment Period or at the Baseline Visit.

### **4.4. Lifestyle Guidelines**

Subjects should maintain their normal daily routine, including stable doses of permitted medications and exercise program. Subjects are also permitted to continue with non-pharmacologic activities (eg, massage, physical therapy) during the trial. Subjects should be cautioned against initiating or altering strenuous exercise regimens during the study as this may influence efficacy and laboratory results. Subjects will be advised to avoid elective surgery (eg, oral surgery) during the course of the study if possible; the study clinician should be contacted for discussion prior to the surgery whenever possible. Subjects who undergo joint replacement or arthroplasty will be discontinued from study treatment and followed in a substudy as described in [Appendix 16](#).

All female subjects who are of childbearing potential and are sexually active and at risk of pregnancy must agree to use one (1) highly effective method of contraception consistently and correctly for the duration of the active treatment period and for 112 days (16 weeks) after the last dose of investigational product. The investigator or his or her designee, in consultation with the subject, will confirm that the subject has selected the most appropriate method of contraception for the individual subject from the permitted list of contraception methods (see below) and instruct the subject in its consistent and correct use. Subjects need to affirm that they meet the criteria for correct use of one of the selected methods of contraception. The investigator or his/her designee will discuss with the subject the need to use highly effective contraception consistently and correctly according to the [Schedule of Activities](#) (SOA) and document such conversation in the subject's chart. In addition, the investigator or his or her designee will instruct the subject to call immediately if the selected contraception methods are discontinued or if pregnancy is known or suspected in the subject or the subject's partner.

Highly effective methods of contraception are those that, alone or in combination, result in a failure rate of less than 1% per year when used consistently and correctly (ie, perfect use) and include the following,

1. Established use of hormonal methods of contraception is allowed provided the subject plans to remain on the same treatment throughout the entire study and has been using that hormonal contraceptive for an adequate period of time to ensure effectiveness. Acceptable methods include:
  - combined (estrogen and progestogen-containing) hormonal contraception associated with inhibition of ovulation:
    - oral
    - intravaginal
    - transdermal
  - progestogen-only hormonal contraception associated with inhibition of ovulation‡:
    - oral
    - injectable
    - implantable

---

‡ Progestogen-only oral hormonal contraception where inhibition of ovulation is not the primary mode of action is not accepted as a highly effective method.

2. Correctly placed intrauterine device (IUD) or intrauterine hormone-releasing system (IUS).
3. Bilateral tubal occlusion.
4. Vasectomised partner provided that the partner is the sole sexual partner of the trial participant and that the vasectomised partner has received medical assessment of the surgical success.
5. Sexual abstinence, defined as refraining from heterosexual intercourse during the entire period of risk associated with the study treatments. The reliability of sexual abstinence needs to be evaluated in relation to the duration of the clinical trial and the preferred and usual lifestyle of the subject.

NOTE: Sexual abstinence, defined as completely and persistently refraining from all heterosexual intercourse (including during the entire period of risk associated with the study treatments) may obviate the need for contraception ONLY if this is the preferred and usual lifestyle of the subject.

#### **4.5. Sponsor's Qualified Medical Personnel**

The contact information for the sponsor's appropriately qualified medical personnel for the trial is documented in the study contact list located in the study manual.

To facilitate access to appropriately qualified medical personnel on study related medical questions or problems, subjects are provided with a contact card. The contact card contains, at a minimum, protocol and investigational compound identifiers, subject study number, contact information for the investigational site and contact details for a contact center in the event that the investigational site staff cannot be reached to provide advice on a medical question or problem originating from another healthcare professional not involved in the subjects participation in the study. The contact center number can also be used by investigational staff if they are seeking advice on medical questions or problems, however it should be only used in the event that the established communication pathways between the investigational site and the study team are not available. It is therefore intended to augment, but not replace the established communication pathways between the investigational site and study team for advice on medical questions or problems that may arise during the study. The contact center number is not intended for use by the subject directly and if a subject calls that number he or she will be directed back to the investigational site.

#### **5. STUDY TREATMENTS**

For the purposes of this study, and per International Conference on Harmonization (ICH) guidelines investigational product is defined as a pharmaceutical form of an active ingredient or placebo being tested or used as a reference in a clinical trial, including a product with a marketing authorization when used or assembled (formulated or packaged) in a way different from the approved form, or when used for an unapproved indication, or when used to gain further information about an approved use (ICH E6 1.33).

### 5.1. Allocation to Treatment

Following implementation of protocol Amendment 3, subjects will be randomized at Baseline to one of the following treatments:

Treatment Group
1. Matching placebo for tanezumab SC once every 8 weeks x 3 administrations
2. Tanezumab 20 mg SC once every 8 weeks x 3 administrations

Subjects will be randomly assigned in a 1:1 ratio to the above treatment regimens according to a computer generated randomization code. Randomization will be stratified by (i) tumor aggressiveness (assessed by Eastern Cooperative Group [ECOG] performance status and (ii) presence/absence of concomitant anticancer treatment (eg, chemotherapy or hormonal therapy or anti-hormonal therapy). Randomization will be coordinated centrally through Interactive Response Technology (IRT). The system will provide subject identification numbers at Screening, which are subsequently linked to the treatment assignments at Randomization. A copy of the randomization code will be maintained by the sponsor by a person(s) who is independent of the trial conduct. It is the responsibility of the Principal Investigator to ensure that the subject is eligible for participation in the study before requesting Randomization. The study site will obtain the subject's randomization number and treatment assignment from the IRT. Further details are provided in the Pharmacy Manual.

Subjects randomized to the 10 mg dose treatment arm who are in the double-blind treatment period at the time of implementation of Amendment 3 will be administered 20 mg for any remaining doses. This will be managed through the IRT drug dispensing system in such a way as to not unblind anyone currently blinded during the study (eg, site staff, subject, sponsor study staff).

**Table 3. Stratification Randomization Scheme**

Randomization Strata	Tumor Aggressiveness*	Concomitant anticancer treatment**
1	More aggressive	Present
2	More aggressive	Absent
3	Less aggressive	Present
4	Less aggressive	Absent
* Screening ECOG performance status score of 0 or 1 corresponds to "less aggressive" tumor; Screening ECOG performance status score $\geq 2$ corresponds to "more aggressive" tumor;		
**Concomitant anticancer treatment as described in Section 5.8.2 .		

### 5.2. Breaking the Blind

This is a randomized, double-blind, parallel group study. The subjects, investigators, other clinical site staff, Clinical Research Associate (CRA), and staff directly involved with the study at Pfizer and its designees will be blinded to subject assignment.

At the initiation of the study, the study site will be instructed on the method for breaking the blind. The method will be either a manual or an electronic process. Blinding codes should

only be broken in emergency situations for reasons of subject safety. Whenever possible, the investigator or sub-investigator consults with a member of the study team prior to breaking the blind. When the blinding code is broken, the reason must be fully documented and entered on the case report form (CRF).

### **5.3. Subject Compliance**

All doses of SC investigational product will be administered by the appropriately designated study staff at the investigational site. Tanezumab SC or matching placebo SC dosing will be recorded on the appropriate CRF. Because tanezumab or matching placebo will be administered by site staff, subject compliance with SC treatment is not anticipated to be an issue.

Compliance with background opioid therapy from Day 1 to Week 8 will be calculated within the IRT for one regimen. If more than one concomitant opioid is used, manual calculation by the sponsor will be undertaken to determine background opioid therapy dose.

### **5.4. Investigational Product Supplies**

#### **5.4.1. Dosage Form(s) and Packaging**

Tanezumab and matching placebo for tanezumab will be supplied by the sponsor or designee.

Tanezumab drug product and matching placebo for SC administration will be supplied in a single-use pre-filled syringe (PFS) that should be stored refrigerated at 2-8°C.

##### **5.4.1.1. Tanezumab**

Tanezumab 20 mg is presented as a sterile solution for subcutaneous administration, packaged in a glass PFS. Each PFS contains a sufficient amount of tanezumab to provide the intended dose of drug at a concentration of 20 mg/mL. Each PFS is packaged in an individual carton. Each PFS has a unique container number.

Tanezumab 10 mg is presented as a sterile solution for subcutaneous administration, packaged in a glass PFS. Each PFS contains a sufficient amount of tanezumab to provide the intended dose of drug at a concentration of 10 mg/mL. Each PFS is packaged in an individual carton. Each PFS has a unique container number.

##### **5.4.1.2. Placebo for Tanezumab**

Placebo for tanezumab is presented as a sterile solution for subcutaneous administration, packaged in a matching glass PFS. Each PFS is packaged in an individual carton. Each PFS has a unique container number.

Only tanezumab 20 mg and matching placebo for tanezumab will be supplied following implementation of protocol Amendment 3. Subjects randomized to the 10 mg dose treatment arm and who are in the double-blind treatment period at the time of implementation of Amendment 3 will be administered 20 mg for any remaining doses. Subjects who are randomized following implementation of protocol Amendment 3 will receive either tanezumab 20 mg or matching placebo.

#### **5.4.2. Preparation and Dispensing**

See the Drug Administration Instructions (DAI) for instructions on how to prepare tanezumab SC and matching placebo SC for administration. Investigational product should be prepared and dispensed by an appropriately qualified and experienced member of the study staff (eg, physician, nurse, physician's assistant, practitioner, or pharmacist) as allowed by local, state, and institutional guidance.

#### **5.5. Administration**

Tanezumab or matching placebo will be administered via SC injection by an appropriately qualified and experienced member of the study staff (eg, physician, nurse, physician's assistant, practitioner, or pharmacist) as allowed by local, state, and institutional guidance and in facilities which can handle allergic reactions. All subjects will receive 1 mL of study medication administered as a SC injection. Subcutaneous injections are to be administered in the abdomen or anterior aspect of the thigh. Selection of the SC injection site for each injection will be at the discretion of the investigator taking into account subject preferences when possible. The SC injection should not be administered in areas where the skin is burned, reddened, inflamed, swollen, or scarred.

o Subcutaneous injection administered via any route other than subcutaneous (i.e. intramuscular, intravenous), is a medication error.

o Syringe (medical device) malfunction is a medication error (e.g. syringe/plunger breaks during administration).

Refer to section [8.4 Medication Errors](#) for additional information.

Full dosage and administration instructions will be provided in the Pharmacist Manual. All local/state/federal laws must be complied with in assigning administration duties.

#### **5.6. Investigational Product Storage**

The Pharmacy Manual will provide complete details on storage and handling.

The investigator, or an approved representative, eg, pharmacist, will ensure that all investigational products are stored in a secured area with controlled access under required storage conditions and in accordance with applicable regulatory requirements.

Investigational product should be stored in its original container and in accordance with the label. See the Pharmacy Manual for storage conditions of the product. Tanezumab and matching placebo will be shipped and stored at a temperature between 2° and 8°C and protected from light.

Storage conditions stated in the single reference safety document (ie, the Investigator Brochure) may be superseded by the storage conditions stated in the labeling.

Site systems must be capable of measuring and documenting (for example, via a log), at a minimum, daily minimum and maximum temperatures for all site storage locations (as

applicable, including frozen, refrigerated and/or room temperature products). This should be captured from the time of investigational product receipt throughout study. Even for continuous monitoring systems, a log or site procedure which ensures active evaluation for excursions should be available. The intent is to ensure that the minimum and maximum temperature is checked each business day to confirm that no excursion occurred since the last evaluation and to provide the site with the capability to store or view the minimum/maximum temperature for all non-working days upon return to normal operations. The operation of the temperature monitoring device and storage unit (for example, refrigerator), as applicable, should be regularly inspected to ensure it is maintained in working order.

Any excursions from the product label storage conditions should be reported upon discovery. The site should actively pursue options for returning the product to labeled storage conditions, as soon as possible. Deviations from the storage requirements, including any actions taken, must be documented and reported to the sponsor. Once an excursion is identified, the investigational product must be quarantined and not used until the sponsor provides permission to use the investigational product. It will not be considered a protocol deviation if the sponsor approves the use of the investigational product after the temperature excursion. Use of the investigational product prior to sponsor approval will be considered a protocol deviation.

The dispensing or administration of expired, quarantined, or improperly stored medication without prior approval from Pfizer Pharmaceutical Sciences (e.g. investigational product storage temperature excursion where subject was dosed with unacceptable drug per Pharmaceutical Sciences) is a medication error.

Refer to section [8.4 Medication Errors](#) for additional information.

Specific details regarding information the site should report for each excursion will be provided to the site.

## **5.7. Investigational Product Accountability**

The investigator or designated personnel must maintain adequate records documenting the receipt, use, loss, or other disposition of the drug supplies.

### **5.7.1. Destruction of Investigational Product Supplies**

The sponsor or designee will provide guidance on the destruction of unused investigational product (eg, at the site). If Pfizer authorizes destruction to take place at the trial site, the investigator must ensure that the materials are destroyed in compliance with applicable environmental regulations, institutional policy, and any special instructions provided by Pfizer. Destruction must be adequately documented.

## **5.8. Concomitant Treatment(s)**

### **5.8.1. Concomitant Treatment Prohibited During the Study**

#### **5.8.1.1. Prohibited Background Opioid Treatment**

The following opioids are not permitted in this study:

butorphanol*	meperidine*
nalbuphine*	pentazocine*
propoxyphene **	
opioids in combination with non-opioids (such as acetaminophen or NSAIDs)***	

\* Use not recommended by NCCN Guidelines;

\*\* Withdrawn from some major markets due to safety concerns

\*\*\* Opioids in combination with acetaminophen may be permitted as standard of care analgesia from Week 8 onwards. Opioid-NSAID combinations are prohibited throughout the study until at least 16 weeks have passed since the last dose of study medication (Week 32 or Early Termination Visit 2).

Permitted background opioid regimens are described in [Section 5.8.2.1](#).

### 5.8.1.2. Prohibited Non-opioid Analgesics

The use of analgesics (other than background opioids and permitted uses described in [Sections 5.8.2](#)) is prohibited throughout the study beginning 48 hours (or 5 half-lives, whichever is longer) prior to the start of the Baseline Assessment Period and ending at Week 8.

Use of NSAIDs and COX-2 selective inhibitors, both prescription or over-the-counter (OTC) is prohibited through Week 32 except for occasional use. Management of subjects' NSAID use is described below ([Section 5.8.1.2.1](#)). Intra-articular injection of corticosteroids to any major joint within 30 days prior to the Baseline Assessment Period through Week 32 is prohibited.

Unless the following drugs were started at least 30 days prior to the first day of the Baseline Assessment Period and are maintained at a stable dose, use of concurrent adjuvant analgesics such as single-agent acetaminophen (paracetamol), serotonin norepinephrine reuptake inhibitors (SNRI), tricyclic antidepressants, anticonvulsant medication, corticosteroids, or muscle relaxants is prohibited through Week 8.

Refer to [Appendix 7: Half-Lives of NSAIDs and Other Analgesics](#), for a detailed washout schedule for analgesic medications. Sites must consult product labeling and conduct a taper according to the product instructions if a taper is required.

#### 5.8.1.2.1. Guidelines for Management of Subjects Reporting NSAID Use

Limited concomitant use of prescription or OTC NSAIDs may be allowed on an occasional basis for self-limiting conditions not related to cancer pain. However, they must not be taken within 48 hours of a study visit where efficacy assessments are being collected. Study management should be contacted for approval prior to use whenever possible, and all doses and days of use must be recorded on the concomitant analgesic CRF.

NSAID use should not exceed a total of 36 days between Day 1 (Baseline) and Week 32 and the aggregate usage of NSAIDs during any one dosing interval (defined as the period of 8 weeks between 2 SC doses) should not exceed 10 days.

Subjects who report concomitant use of prescription or OTC NSAIDs during the study prior to Week 32 will be managed as per the following guidelines:

- Subjects who report concomitant use of NSAID should be interviewed by study site personnel to determine the reason for use and if the subject anticipates being able to comply with concomitant medication restrictions in the future. Subjects who indicate they are taking NSAIDs because of insufficient cancer pain relief or who indicate that they cannot or will not be able to comply with concomitant medication restrictions will be withdrawn from study treatment and entered in the Early Termination Follow-Up period (refer to [Section 6.4](#)).
- Subjects who reported greater than 10 days (aggregate total) of concomitant NSAID use (any dosage of NSAIDs) in a SC dosing interval and who after counseling report further concomitant NSAID use should be withdrawn from study treatment and entered in the Early Termination Follow-Up period (refer to [Section 6.4](#)).

After Week 32, there are no restrictions on NSAID use provided the NSAID dosing is prescribed according to its approved label.

Subjects will be instructed that many over-the-counter medications contain NSAIDs and to be aware of this during their selection of OTC medications. Subjects who report concomitant NSAID use will be requested to provide details of the usage (dosage and reasons for use) which will be recorded in the appropriate concomitant medication case report form (CRF).

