### **6.3. Safety Follow-Up Period**

Subjects who enter the Safety Follow-Up period after completion of the Double-Blind Treatment period and the Week 24 visit will be followed for an additional period of 24 weeks. This will include 2 clinic visits (Weeks 32 and 48) and 4 telephone contacts (Weeks 28, 36, 40 and 44) between site staff and enrolled subjects. For Japan only, the Week 40 visit will be in-clinic.

During the Safety Follow-Up period (after the Week 24 visit), the subject will no longer report cancer pain scores in the IRT (subject diary) for purposes of efficacy assessments. The subject will only provide a weekly assessment of joint pain (shoulders, hips and knees) and any NSAID use via IRT using a 24-hour recall period through Week 48.

From Week 24 to Week 32, the subject will continue to use opioids for cancer pain treatment (which as noted in Schedule of Activities [Table 1](#) (footnote 1) may have been liberalized

beginning as early as Week 8). Any needed opioid dose adjustments during this period should continue to follow accepted clinical guidelines (as described in [Section 6.1.1.2.4](#)).

If needed, beginning at Week 32, treatment with NSAIDs may proceed without restriction, but within approved label instructions.

At Week 48, the subject will return for the final End-of-Study clinic visit. At this visit, all End-of-Study procedures are to be completed, including general physical **CCI** **CCI** x-rays of each knee, hip and shoulder, laboratory assessments and other safety assessments as described in the [Schedule of Activities](#). X-rays of each shoulder, hip and knee as well as any additional joint that was imaged at Screening or identified as at risk during the study will be obtained. These images will be sent to the blinded Central Reader for review.

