### NSAIDs & COX-2 selective inhibitors:

Use of NSAIDs and COX-2 selective inhibitors, both prescription or over-the-counter (OTC) is prohibited during the study until Week 32 except for occasional use.

Limited concomitant use of prescription or OTC NSAIDs may be allowed on an occasional basis for self-limiting conditions not related to cancer pain. However, they must not be taken within 48 hours of a study visit where efficacy assessments are being collected. NSAID use should not exceed a total of 36 days between Day 1 (Baseline) and Week 32 and the aggregate usage of NSAIDs during any one dosing interval (defined as the period of 8 weeks between 2 SC doses) should not exceed 10 days.

Management of NSAID use is described in Section 5.8.1.2.1. Washout period guidance is provided in [Appendix 7](#).

Daily low dose aspirin ( $\leq 325$  mg as per local prescribing practice) therapy for cardiovascular prophylaxis is permitted without restriction.

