### **Corticosteroids:**

Unless they were started at least 30 days prior to the first day of the Baseline Assessment Period and are maintained at a stable dose, oral or intramuscular corticosteroids used as concomitant analgesics are prohibited from the start of the Baseline Assessment Period through Week 8.

Oral or intramuscular corticosteroids used as concomitant analgesics starting less than 30 days prior to the Baseline Assessment Period must be washed out during the Screening Period for a period of at least 48 hours or 5 times the half-life of the particular corticosteroid (whichever is greater) before starting the Baseline Assessment Period. Intra-articular injection of corticosteroids to any major joint within 30 days prior to the Baseline Assessment Period through Week 32 is prohibited.

Limited use of oral, intramuscular or intravenous corticosteroids for non-analgesic purposes such as prophylaxis or treatment of chemotherapy-induced nausea and vomiting is permitted. Topical, inhaled and intranasal corticosteroids are permitted. Refer to [Section 5.8.2.2](#) for details.

Corticosteroid	Permitted	Prohibited
Oral or intramuscular corticosteroids used as concomitant analgesics	If started at least 30 days prior to the first day of the Baseline Assessment Period and maintained at a stable dose	If started within 30 days of the first day of the Baseline Assessment Period. Washout is required prior to the first day of the Baseline Assessment Period, and further use

		is prohibited until Week 8
Oral, intramuscular or intravenous corticosteroids for non-analgesic purposes such as prophylaxis or treatment of chemotherapy-induced nausea and vomiting	Limited use is permitted	-
Intra-articular injection to any major joint	Allowable after Week 32	Prohibited within 30 days prior to the Baseline Assessment Period through to Week 32
Topical, inhaled and intranasal corticosteroids	Permitted throughout study	-

Examples of Corticosteroids	
Generic	Brand
betamethasone	Celestone, Soluspan
cortisone	
dexamethasone	Decadron, Dexacort, Turbinaire
fludrocortisone	Florinef
hydrocortisone	A-hydroCort, Cortef, Hydrocortone, Solu-Cortef
methylprednisolone	Medrol, Solu-Medrol
prednisolone	Orapred, Prelone
prednisone	Cortan, Deltasone, Medicorten

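### The NSAID and intra-articular corticosteroid limits end at Week 32 in some sections and 16 weeks after the last injection in others; the two can differ by weeks when dose 3 is late or the Week 32 visit is early

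*Protocol*

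**What the plan says.** The protocol writes two end-points for the same restriction.

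**Calendar end-point (Week 32; Day 225 ±7 in Table 1).**
- Section 5.8.1.2.1 releases NSAIDs: "After Week 32, there are no restrictions on NSAID use provided the NSAID dosing is prescribed according to its approved label".
- Section 6.3 does the same: "beginning at Week 32, treatment with NSAIDs may proceed without restriction".
- The Appendix 8 corticosteroid table marks injection into a major joint as "Allowable after Week 32".
- Section 5.8.1.2 states no release but ends its bans there. NSAID and COX-2 inhibitor use "is prohibited through Week 32 except for occasional use", and for steroids: "Intra-articular injection of corticosteroids to any major joint within 30 days prior to the Baseline Assessment Period through Week 32 is prohibited".
- The Appendix 8 NSAID text matches: use "is prohibited during the study until Week 32 except for occasional use".

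**Dose-based end-point (16 weeks, 112 days, after the last subcutaneous dose).** This is the rule in Table 1 footnote u, Table 2 footnote f and Section 5.8.2.2.

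**Text that treats the two as one.** Sections 5.8.1.1 and 5.8.2.5 and the Appendix 8 opioid entry give the 16-week rule and add a parenthesis naming Week 32 or Early Termination Visit 2 as the point at which it is met.

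Section 5.8.1.2.1 also counts its NSAID-day cap to Week 32 ("NSAID use should not exceed a total of 36 days between Day 1 (Baseline) and Week 32"), and its handling rules cover NSAID use reported "during the study prior to Week 32 will be managed as per the following guidelines".

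**The concern.** Section 5.8.2.5 explains the 16 weeks: tanezumab should have been eliminated, and joint risk should be kept low, before regular NSAIDs or intra-articular steroids resume. That purpose depends on time since the last injection, not on the study week. The protocol itself allows dose 3 to be late, by up to 14 days for unresolved dysesthesia or allodynia (Section 7.4.1) or up to 12 weeks after the previous dose during a sympathetic-function work-up (Section 7.4.3). Table 1 also lets the Week 32 visit fall 7 days early.

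In those cases a site that follows Section 5.8.1.2.1 or 6.3 to the letter can release NSAIDs before the dose-based point, while a site that follows footnote u would not. Both would be complying with the protocol. Under the two hold rules, the subjects exposed to the discrepancy would be those whose dose was delayed because of an adverse event.

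**Working it through.** **Inputs.** Doses 2 and 3 on Days 57 and 113, each ±3 days; Week 32 visit on Day 225 ±7 (Table 1). Longest hold 14 days (Section 7.4.1). Longest interval 12 weeks, or 84 days (Section 7.4.3). Half-life about 21 days (Section 3). Complete washout described as 5 half-lives (Table 2 footnote d), so 5 × 21 = 105 days.

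**Reproducing the protocol's equivalence.** 225 - 113 = 112 days = 16.0 weeks. On nominal days Week 32 and the dose-based point coincide exactly. At that point 112 / 21 = 5.33 half-lives have passed.

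**Departures, if Week 32 is not re-timed.** Days since dose 3 = visit day minus dose-3 day; shortfall = 112 minus that figure.

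| Case | Dose 3 | At Day 225 | Shortfall | At Day 218 | Shortfall | 16-week point |
|---|---|---|---|---|---|---|
| On schedule | Day 113 | 112 d | 0 | 105 d | 7 d | Day 225 |
| 14-day hold | 113 + 14 = Day 127 | 98 d | 14 d (2 wk) | 91 d | 21 d (3 wk) | Day 239 |
| 12-week interval | 57 + 84 = Day 141 | 84 d | 28 d (4 wk) | 77 d | 35 d (5 wk) | Day 253 |

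In half-lives at Day 225: 98 / 21 = 4.67 after the 14-day hold and 84 / 21 = 4.0 after the 12-week interval. Both are below the protocol's 5. With simple exponential decay, the fraction remaining is 2.5% on schedule, 3.9% after the hold and 6.25% after the 12-week interval.

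**Windows alone, no hold.** Dose 3 at its late edge (Day 116) and the visit at its early edge (Day 218): 218 - 116 = 102 days, 10 days short of 112.

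**Late edge of the visit window (Day 232).** 232 - 127 = 105 days and 232 - 141 = 91 days, so even the latest in-window visit does not absorb a full 14-day hold or a 12-week interval.

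**These are not maxima.** The 12-week case takes dose 2 on Day 57. With dose 2 on Day 60, dose 3 could fall on Day 144; 144 + 112 = Day 256, which is 31 days after Day 225.

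**The case against.** The strongest reply is that the protocol means Week 32 as shorthand for the 16-week point, and that visits move with the dose. The parentheses in Sections 5.8.1.1 and 5.8.2.5 and Appendix 8 support the first part. For the second, Section 3 places the end-of-treatment visit 8 weeks after the last dose and starts follow-up there, Section 6.3 gives completers a further 24 weeks from that visit, and Section 6 asks for visits to be scheduled by dosing date as far as possible. Without re-timing, the Week 24 visit on Day 169 would come only 169 - 127 = 42 or 169 - 141 = 28 days after dose 3, against Section 3. Re-timing is therefore the likelier reading after a hold, and this narrows the problem. It does not remove it: Table 1 prints Day 225 ±7, no sentence re-counts Week 32, and the windows leave a shortfall without any hold.

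It is also true that the dose-based rule stands on Table 1's own NSAID row, that occasional NSAID use is allowed in any case, and that NSAID use is recorded to Week 48.

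A reader might infer that a subject still restricted after Week 32 is left without any safeguard, because the 36-day cap and the handling rules stop there. The protocol does not support much of that. The sanction in Section 5.8.1.2.1 is withdrawal from study treatment, and after the third and last dose there is none left to withdraw. Its 10-day limit applies to intervals between two injections, which are also over.

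**Conclusion.** The inconsistency is real and small. Following Section 5.8.1.2.1 or 6.3 literally can release NSAIDs before the 16-week point that the protocol sets for drug elimination and joint safety, and the Appendix 8 table can do the same for intra-articular steroids. If Week 32 is not re-timed, the release is 2 weeks early after a 14-day hold and 4 weeks early after a 12-week interval on nominal days, or 3 and 5 weeks with a Day 218 visit. Windows alone can cost 10 days.

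A reader might take 2 and 4 weeks as the worst case; they are nominal-day figures, as the window and dose-2 examples show. A reader might also infer that subjects will in practice get NSAIDs too early. The protocol does not show this: its visit rules lean towards re-timing, and the number of subjects with a late dose 3 or an early Week 32 visit cannot be derived from it. The half-life figures rest on the approximate 21 days. Nothing here touches the Week 8 primary endpoint, alpha or the sample size.

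**What to change.** Make the dose-based rule govern.

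- In Section 5.8.1.2 (both bans), the release sentence of Section 5.8.1.2.1, Section 6.3, the Appendix 8 NSAID prohibition, and the Appendix 8 intra-articular entries (the text and both table cells), replace the Week 32 end-point with *until at least 16 weeks (112 days) after the last SC dose*, adapting the grammar where the sentence states a release.
- In Sections 5.8.1.1 and 5.8.2.5 and the Appendix 8 opioid entry, delete the parenthesis that equates the 16 weeks with Week 32 or Early Termination Visit 2, or begin it with *nominally*.
- Leave the 36-day cap and the handling rules as they are. Putting the dose-based phrase into the cap would give its counting period no fixed end.

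That is 2 + 1 + 1 + 1 + 3 = 8 end-points and 3 parentheses, 11 wording edits in all. No new data are needed, because dosing is already recorded on the case report form (Section 5.3).

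The cost falls on subjects with a late dose 3 or an early Week 32 visit. They wait a few weeks longer for regular NSAIDs or an intra-articular steroid, for example to Day 239 after a 14-day hold or Day 253 after a 12-week interval. A subject dosed on Day 113 and seen on Day 225 notices no change.
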